The applicant proposes a prospective, randomized controlled open-label trial known as SUSTAIN, or **Stop Community MRSA Colonization among Patients**. The SUSTAIN trial will evaluate MRSA decolonization and determine differences in the prevalence of MRSA colonization (main outcome) at 6 months. Patients with a known history of MRSA colonization will be recruited from the (JHUAS). After consent and baseline MRSA screening, index subjects (50 per arm), described below, will be randomized to a standardized decolonization protocol directed at both the individual and their household and/or sexual partner(s) or a decolonization for the individual alone. Each index (i.e. person living with HIV within the Johns Hopkins Moore Clinic) will be approached for enrollment in the study. Information flyers, study rotating digital kiosk and provider referral will be used for recruitment. We will also search the Johns Hopkins Hospital Epidemiology and Infection Control (HEIC) database for known MRSA colonized individuals and contact former study participants.

SUSTAIN Standardized Decolonization Regimen (intervention):

According to the IDSA clinical practice guideline⁷, the standardized decolonization regimen for the nose and groin will include a 5-day course of nasal mupirocin calcium 2% cream applied inside the nose twice daily, plus a 4% chlorhexidine gluconate (soap) used in the shower/bath every day for 10 days^{20,19}. For individuals colonized within the throat we will add chlorhexidine gluconate oral rinse 0.12% used in a gargle and spit fashion twice daily for 7 days. A standardized educational session on use and accompanying CDC instructional frequently asked questions handout and an instructional medication sheet will be provided. For children < 7 years of age, we will provide decolonization using 4% chlorhexidine gluconate (soap) used in the shower/bath every day for 10 days. No antimicrobial cream or gargle will be utilized. If an adult household member or sexual partner is colonized at a single site, he or she will receive the soap, rinse and Mupiricin cream. If he/she is not colonized at any body site, no decolonization regimen will be provided.

Date: 6/10/13

Principal Investigator: [name], MPH, NP

Application Number: NA_00079147

ENROLLMENT:

Patient Population/Setting:

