Randomization: This study has taken into consideration the guidelines for reporting of clinical trials as recommended by the CONSORT report²¹ to inform the study design (Figure 1). After recruitment and informed consent, patients will undergo pre-randomization screening. Patients who screen negative for MRSA at this point will have completed the protocol. Patients screening MRSA positive will then be randomized to the two possible open-label treatment arms. Arm 1 will include randomization to standardized decolonization protocol of the individual plus household and/or sexual partner(s). Arm 2 will include randomization to standardized decolonization protocol for the individual patient alone. Randomization will occur through computerized random number generation in Stata, version 11. A simple parallel randomization design will be utilized. Once developed, this randomization scheme will be placed in an individually concealed envelope. The RA will not be aware of the randomization scheme of the individual envelopes until opened in front of the patient on the day of randomization.

Figure 1: SUSTAIN Study Design Overview

* The household members and/or sexual contacts will be consented prior to initiation of the decolonization protocol

Data Collection Measures:

The risk factor questionnaire used in the proposed study has been thoroughly evaluated with over 1000 subjects (50% with HIV). Questions have been added or removed as applicable to this patient population. The

Date: 6/10/13

Principal Investigator: [name], MPH, NP

Application Number: NA_00079147

questions in the protocol can easily be administered by a study team member in 20 minutes. The questionnaire has been thoroughly evaluated by experts in the field of hospital epidemiology and infection control for content validity. In addition to the subject questionnaire, each instrument contains an additional section for the research team to interrogate the patient's medical record to verify specific pieces of the medical history such as CD4 count, medication history, viral load, etc. Adolescents will complete the questionnaire, but for children younger than 13, we will have the parent complete the risk factor questionnaire. Each document ends with a microbiology results page for the principle investigator (PI) to complete.

MRSA Screening Procedures:

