Individuals, 21 years of age and older, of all racial and ethnic groups, receiving care within the JHUAS who have a prior history of MRSA colonization are eligible to participate as the index HIV positive subject. This person should have at least two members in the household and/or a sexual partner. A post-consent pre-randomization screening phase will be completed to ensure subjects are MRSA colonized. In addition to these criteria subjects must be willing to be randomized to either arm of the study, including randomization to household and/or sexual partner evaluation. Sexual partners and/or household members will also be required to provide informed consent. Subjects and their contacts must have no documented or reported allergies to any agent used in the standardized decolonization regimen. Parental assent will be required for household members less than 7 years of age. Exclusion criteria include: allergy to any component of decolonization protocol; individuals who live alone and have no active sexual partners; individuals who are unable to provide written informed consent.

Recruitment Strategy:

Study team members will speak with JHUAS providers to discuss the study and seek patient referrals (i.e. index patient). A HIPAA waiver will be sought in order to obtain a list of patients with a known history of MRSA colonization from Johns Hopkins Hospital Epidemiology and Infection Control Department. In the HIPAA waiver, we are asking to contact the patient's provider in the Moore Clinic to inform of the patient's eligibility for the study prior to the subject seeing his or her provider in clinic. The provider could then inform the patient of their eligibility and ask if we can contact them about the study. [name] previous work has already identified over 70 JHUAS patients with a known history of MRSA colonization. The patients in this prior study have agreed to be contacted for future studies when they signed informed consent. We have included details for a HIPAA waiver to evaluate this information in this IRB application. We have also

Date: 6/10/13

Principal Investigator: [name], MPH, NP

Application Number: NA_00079147

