completed a HIPPA form 3 to document that we have permission to contact the index patient again for future studies on MRSA in this patient population. These index HIV positive patients will be approached for study screening during a clinic visit or via telephone to schedule a study visit. Index HIV positive patients will receive a \$25.00 gift card on completion of the protocol. We will offer household members a single gift card of \$50.00 regardless of the number of participants.

Recruitment of Household Members/Sexual Contacts:

To avoid disclosure of personal health information (PHI), the index patient will be given the option for a home visit by the research team or they and their household members and sexual contacts can be screened at the Clinical Research Unit (CRU). We will work closely with the IRB/DSMB to protect subject's PHI. Recruitment of the primary sexual partner and or family members will occur by referral from the enrolled subject. During the risk factor evaluation, the subject will be asked, "In the last 6 months have you had sex?" We then ask several follow-up questions on sexual activity. The enrolled subject will be asked to refer his/her primary sexual partner, the person the subject most frequently engages in anal, vaginal or oral sex with, to the study. At no time will study data of either the primary subject or the subject's sex partner be shared by the research team to the other participant regardless of their awareness of the other partner's status. Neither the screening process, nor the questionnaire reveals any information about HIV status.

6. Drugs/Substances/Devices

According to the IDSA clinical practice guideline⁷, the standardized decolonization regimen for the adult colonized in either the nose or groin will include a 5-day course of nasal mupirocin calcium 2% applied inside the nose twice daily, plus a 4% chlorhexidine gluconate (soap) used in the shower every second day for 10 days²⁰. For individuals colonized within the throat we will add chlorhexidine gluconate oral rinse 0.12% used in a gargle and spit fashion twice daily for 7 days. A standardized educational session on use and accompanying instructional handout will be provided. Children under 6 months will not be included in the study. For children over 6 months and <7 years of age 4% chlorhexidine gluconate (soap) used daily for 10 days. For children over the age of 7, we will follow the same protocol as adults.

7. Study Statistics

ANALYSIS:

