------	----------------	-----------------	--------	--------

Date: 6/10/13

Principal Investigator: [name], MPH, NP

Application Number: NA_00079147

Task	Preparation	Enrollment	Enrollmen t	Follow- Up
IRB Process				
Identify/Train Research and Lab Assistants				
Recruitment/Informed Consent/Screening				
Decolonization and Study Visits				
Surveillance for Clinical Infection				
Microbiologic Evaluations				
Data Entry and Statistical Analysis				
Present at Meetings and Publish Data				
Preparation of application for R01				

8. Risks

Potential Risks:

The risks for this study are minimal. There is a very small risk of bleeding associated with swabbing mucosal membranes; however, our institution has a long standing history of obtaining nares surveillance cultures for MRSA without any reported adverse events. Standard precautions will be applied for protection of the RA and/or clinician during specimen collection. All swabs will be collected in a private exam room. A clinic gown will be provided for the patient to protect modesty and privacy during collection. A female chaperone will be present at all times when specimens are being obtained from a female patient by a male clinician as is standard in our clinic during gynecologic evaluations.

Allergic reactions to mupiricin and/or chlorhexidine are rare. Patients with known allergy will be excluded from the study. All agents are FDA approved for the purposes used in this study.

Mupiricin Cream Possible Adverse Effects:

Local adverse effects may be associated with mupirocin application. Mupirocin ointment or cream may commonly cause itching, pain, stinging, and burning. Local effects from the nasal formulation have included epistaxis, rhinitis, taste perversion, pharyngitis, burning, and cough. Gastrointestinal side effects have included nausea (1.1%), abdominal pain (<1%), and diarrhea (<1%). Dry mouth has been reported with mupirocin nasal (<1%). Nervous system side effects associated with intranasal mupirocin have included headache (9%). Dizziness has been reported with mupirocin ointment (<1%). Ocular side effects associated with mupirocin nasal ointment have included blepharitis (<1%).

Chlorhexidine gluconate Oral Rinse Possible Adverse Effects:

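### Could a contact's refusal or allergy remove a randomized index patient and bias the comparison of arms?

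*Combined protocol and SAP*

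**What the plan says.** Section 5 (Eligibility Criteria) states two conditions on contacts. On consent: "Sexual partners and/or household members will also be required to provide informed consent". On allergy: "Subjects and their contacts must have no documented or reported allergies to any agent used in the standardized decolonization regimen". Neither sentence says what happens to the index if a contact fails the condition. The exclusion list that follows reads "Exclusion criteria include: allergy to any component of decolonization protocol; individuals who live alone and have no active sexual partners", and ends with inability to give written informed consent. Refusal by a contact is not on it. Section 5 also requires the index to accept either arm, including evaluation of the household or sexual partner, before being randomized.

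The order of events is in Section 4. Under Randomization: "Patients screening MRSA positive will then be randomized to the two possible open-label treatment arms". The footnote to Figure 1 says "The household members and/or sexual contacts will be consented prior to initiation of the decolonization protocol", so contact consent is tied to the start of treatment and not to allocation. Under Study initiation after screening, the contact visit is scheduled for indexes already assigned to the household arm, within 14 days of the culture result. Household contacts in both arms are offered screening, but no date is given for Arm 2.

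Section 7 compares the proportions colonized at 6 months with Fisher's exact test, adds a multinomial logistic model, and does not name an analysis set.

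**The concern.** Eligibility criteria normally decide who is randomized. Here two conditions stand under that heading but concern people whom the team may not meet until after the envelope is opened. If they bind the index, a patient could be found ineligible after an open-label allocation. Because the only dated contact step is in Arm 1, this would probably happen more often there, although that is an inference. Removing those patients would take a selected group out of one arm, and the bias could go in either direction.

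If the conditions bind only the contact, the index stays but its household may go partly or wholly untreated, and the contrast between arms shrinks. With no analysis set named, staff who know the allocation might appear free to choose between these courses case by case.

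**Working it through.** **Whom do the conditions bind?**

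- *Consent.* The sentence stands close to the one on parental assent for young household members, which is plainly a condition on that person's own entry. The consent procedures in Section 4 have each adult contact sign individually. The exclusion list has no entry for contact refusal.
- *Allergy.* The sentence does join subjects and contacts. Section 8, however, applies the exclusion to the patient: "Patients with known allergy will be excluded from the study".
- *Expected uptake.* The household gift card is a single payment "regardless of the number of participants" (Sections 5 and 10), and limitation 4 in Section 7 accepts that not every contact can be reached. Under the regimen in Section 4, an adult contact who screens negative goes untreated: "If he/she is not colonized at any body site, no decolonization regimen will be provided". An Arm 1 index with an untreated contact is therefore an ordinary case under this strategy.

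These passages favour the reading in which the index stays in the trial.

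**Inputs for sizing.** From Section 7: 60% colonized in Arm 2, 30% in Arm 1, alpha 0.05 (taken as two-sided), 41 per arm, 20% attrition, 50 per arm enrolled. The documents give no rate of contact refusal or contact allergy. The share of Arm 1 affected, *q*, is assumed to be 5%, 10% or 20%. The risk in excluded indexes, *r*, is assumed to lie between 40% and 90%.

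**The plan's own figure.** The two-proportion formula with pooled variance and no continuity correction gives 42 per arm for 80% power, and 79.0% power at 41. The stated 41 for approximately 80% is reproduced. After attrition, 50 × (1 − 0.20) = 40 per arm, where Fisher's exact test has 72.5% power. That figure reflects the choice of test and the attrition, before any contact problem.

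**If indexes were dropped from Arm 1 only, with no true effect (60% in both arms).**

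Bias = (0.60 − *q* × *r*)/(1 − *q*) − 0.60. For example, *q* = 0.20 and *r* = 0.90 give (0.60 − 0.18)/0.80 − 0.60 = 0.525 − 0.60 = −0.075. The bias is zero when *r* = 0.60. Fisher rejection rates are by exact enumeration.

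| *q* | n, Arm 1 vs Arm 2 | Bias, *r* = 0.40 to 0.90 | Fisher rejection, *r* = 0.40 / 0.60 / 0.80 / 0.90 |
|---|---|---|---|
| 5% | 38 vs 40 | +1.1 to −1.6 points | 4.0% / 3.9% / 3.9% / 3.9% |
| 10% | 36 vs 40 | +2.2 to −3.3 points | 4.0% / 3.6% / 3.9% / 4.3% |
| 20% | 32 vs 40 | +5.0 to −7.5 points | 5.3% / 3.5% / 5.1% / 7.2% |

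**If all indexes are kept as assigned, with 30% taken as the rate under full contact uptake.**

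With no household benefit in a share *q*, the Arm 1 rate = 0.30(1 − *q*) + 0.60*q*. If half the benefit is kept, 0.60 is replaced by 0.45. Fisher power at 40 per arm:

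| *q* | No benefit kept: Arm 1 rate, power | Half kept: Arm 1 rate, power |
|---|---|---|
| 5% | 0.315, 67.5% | 0.3075, 70.0% |
| 10% | 0.33, 62% | 0.315, 67.5% |
| 20% | 0.36, 51% | 0.33, 62% |

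These losses are upper figures. Section 7 gives 30% as the rate expected in the whole arm, set with feasibility in mind, and does not say that it presumes full uptake. If it already allows for incomplete uptake, the same loss would be counted twice.

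**The case for a change.** The best case for a change is that contact participation is the only planned difference between the arms, so a contact who does not take part is the most foreseeable departure from the design. The allergy sentence names contacts in an eligibility paragraph, no step checks contacts before allocation, and analysis as assigned is nowhere written. The index's willingness to enter either arm does not establish a contact's consent or allergy status. Aim 2 wants an effect size and a fidelity plan for a larger trial, and contact uptake bears on both.

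The textual points stand: the allergy sentence is ambiguous and the analysis set is unnamed. The argument for bias does not follow from them. It needs an event that is both frequent and read as disqualifying the index. Refusal could be frequent, but nothing makes it an index exclusion. Allergy is arguably written as one, but is expected to be rare. The willingness requirement, applied before allocation, should also reduce later failures. Nor is the problem certain to be one-sided: contacts are offered screening in both arms. Figure 1 is not shown, so the sequence rests on the text alone.

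Reporting contact uptake by arm would be informative under Aim 2. The contact numbers on swabs identify only those screened, so a count of refusals would need a simple log. That would describe delivery of the intervention and would not alter the randomized comparison.

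**Conclusion.** No change follows. This is missing detail that an analyst fills sensibly: once randomized, an index is analysed in the assigned arm whatever its contacts do. No stated rule removes such a patient, and most of the relevant passages point to keeping it. Analysis as assigned removes the exclusion bias by itself, without contact consent before allocation. Any reduced effect is then part of what offering the household strategy achieves.

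Even under the unfavourable reading, the size is modest at plausible rates. With 5% or 10% of Arm 1 dropped, the bias is at most 3.3 points in either direction and the Fisher false-positive rate is at most 4.3%. Clear inflation, to 7.2%, needs a fifth of Arm 1 and none of Arm 2 dropped, with 90% risk among those dropped. These figures rest on assumed exclusion shares and risks, on 60% colonization in both arms, and on a two-sided test with 40 per arm before exclusions.

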To assess colonization prevalence among PLWHA, we conducted an epidemiologic evaluation of MRSA among persons within the Johns Hopkins University AIDS Service (JHUAS). The study included 500 subjects (65.8 % male) along with the sexual partners of 35 subjects. The MRSA colonization prevalence was 16.8% among subjects and 37% (17/35) in their sexual partners (unpublished data). These findings demonstrate an exceptional difference in colonization prevalence in PLWHA compared to the US population¹⁰ and supports the need for further research to understand decolonization regimens that evaluate outcomes for individual decolonization only compared to the inclusion household and/or sexual partner interventions. We propose a randomized controlled trial (RCT) among 100 PLWHA (50 per arm) within the JHUAS to evaluate an individual versus household/sexual partner decolonization intervention.

2. Objectives/Aims

The specific aims of the proposed RCT are:

1. To compare a MRSA decolonization protocol for the colonized individual (index) versus the index plus their household member and/or routine sexual partner(s).
H0: Index plus household/sexual partner(s) decolonization will be associated with a lower occurrence of MRSA colonization at 6 months after completion of decolonization protocol.
2. To estimate the intervention effect size and develop an intervention fidelity assessment plan to scale the intervention into a larger multi-city R01 application.
3. To determine the molecular characteristics and antimicrobial susceptibilities of both the clinical and colonizing isolates among index patient as well as household members.

3. Background

Community-associated methicillin resistant *Staphylococcus aureus* (CA-MRSA) greatly impacts health outcomes among PLWHA. Outbreaks of CA-MRSA skin and soft tissue infections have occurred in metropolitan areas throughout the country including San Francisco¹¹, Boston¹² and Dallas¹³. These outbreaks have identified key risk differences for CA-MRSA colonization and/or infection among this population

Date: 6/10/13

Principal Investigator: [name], MPH, NP

Application Number: NA_00079147

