Screening of Adult Household Contacts and Sexual Partners:

All household contacts in both arms of the study will be offered MRSA screening. We will complete the same procedures for adult household contacts and sexual partners described above. Contacts will receive swabs of the same body sites with each swab labeled with the same study ID # as the index case, but with the addition of HC # and SP # to identify household contact and sexual partners respectively. This will assist us with identification and linkage during the molecular epidemiologic evaluation of the isolates.

Screening of Children/Adolescent Household Contacts:

For children/adolescents under 18, we would screen nares, throat and rectum only. All screening of the child up to 12 years of age would be conducted with the parent present. Adolescents will be asked whether or

Date: 6/10/13

Principal Investigator: [name], MPH, NP

Application Number: NA_00079147

not they wish for their parent to be present during the rectal swab. All swabs will be conducted in the presence of two adults (either RA and parent or two RAs). Adolescents between 18 years of age and 21 years of age will receive the adult screening protocol sites.

Study initiation after screening:

After results for the index subject are obtained, a member of [name] team will contact the subject to review the results and randomize the MRSA positive subject into the intervention or control arms. Subjects in the individual arm, will initiate after learning results at the clinic follow-up visit. For individuals assigned to the intervention group, we will schedule a time for a home visit to screen household members or a time in the CRU for evaluation. This screening visit will occur within 14 days of obtaining the original culture results. All household members will then initiate the intervention at the same time.

Microbiological Measures:

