Dependent Variable (DV): The DV is a group of mutually exclusive, non-ordered outcomes which include: negative for *S. aureus*, positive for methicillin susceptible *S. aureus*, positive for methicillin resistant *S. aureus*.

Independent Variables: A thorough search of the available literature has been completed to develop the risk factor questionnaire designed for this study²³. The questionnaire includes: demographic data, medical history, sexual history, substance abuse history, as well as healthcare associated and community-based MRSA risk factors.

Sample Size: Based on prior studies, it appears that the probability of MRSA colonization at 6 months after decolonization ranges from 60% to 80%. Although an exact effect size is not known for individuals with household/sexual partner decolonization, we have considered both feasibility and public health importance. We believe the intervention will achieve a 50% reduction in colonization at 6 months (i.e. 30% colonization [0.30]

Date: 6/10/13

Principal Investigator: [name], MPH, NP

Application Number: NA_00079147

in the arm with individual and household/sexual partner decolonization compared to 60% [0.60] colonization in individual alone arm). **Based on these figures and an alpha of 0.05, the total sample size required to achieve approximately 80% power is 41 per arm.** We anticipate 20% attrition and will oversample by 9 subjects per arm, bringing total sample size to 50 per arm.

Statistical Analysis Plan: Demographic variables will be evaluated using chi-square and Fisher's exact testing as appropriate. Fisher's exact will also be utilized to compare proportion of persons colonized at 6 months. Multinomial logistic regression will be used to determine the odds of subsequent MRSA colonization in the two arms and to determine the magnitude of the effect size between the arms.

LIMITATIONS AND PLAN TO ADDRESS:

As with any clinical trial, this study has possible limitations:

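### The power figure applies a halving to the whole of Arm 1 and makes no allowance for index patients whose contacts receive no regimen; the share affected is not established, and who is treated is stated inconsistently

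*Combined protocol and SAP*

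**What the plan says.** All references are to the combined protocol and SAP.

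- **Effect and power (section 7, Sample Size).** The expected effect is "We believe the intervention will achieve a 50% reduction in colonization at 6 months", that is, 30% in the household/partner arm "compared to 60% [0.60] colonization in individual alone arm". The text adds that at "alpha of 0.05, the total sample size required to achieve approximately 80% power is 41 per arm". It admits that the effect size for household/partner decolonization is not known, and gives 60% to 80% as the range of 6-month colonization in prior studies.
- **Who is treated (section 4, Standardized Decolonization Regimen).** For adult household members and sexual partners: "If he/she is not colonized at any body site, no decolonization regimen will be provided". The soap for children under 7 has no stated culture condition.
- **Text that reads differently.** The last paragraph of section 3 describes testing an intervention given to every member of the household or partner network. In section 4, the paragraph on study initiation after screening has all household members starting the intervention together.
- **Contact carriage (introductory text before section 2).** "The MRSA colonization prevalence was 16.8% among subjects and 37% (17/35) in their sexual partners (unpublished data").
- **Number of contacts (section 5, Eligibility).** "This person should have at least two members in the household and/or a sexual partner".
- **What the arms share (section 4).** "All household contacts in both arms of the study will be offered MRSA screening", and hygiene and cleaning instructions go to all subjects.

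**The concern.** If the section 4 rule applies, an Arm 1 index patient with no treated contact differs from an Arm 2 patient only by a possible delay while contacts are screened. Contact screening and hygiene advice are common to both arms, so such a patient cannot be expected to contribute to the difference. Section 7 makes no allowance for this, and its list of limitations does not mention it.

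Two things are at stake. A null result could be read as failure of household decolonization when, for some unknown share of Arm 1, nothing was added. And Aim 2 passes the estimated effect to a larger trial: without π, that effect is a mixture whose components cannot be separated.

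**Working it through.** **1. The plan's own figure.** With p₂ = 0.60, p₁ = 0.30, mean 0.45, two-sided α = 0.05 (sidedness is not stated, so this is an assumption) and the pooled formula:

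n = [1.960·√(2·0.45·0.55) + 0.842·√(0.60·0.40 + 0.30·0.70)]² / 0.30² = (1.379 + 0.565)² / 0.09 ≈ 42 per arm.

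Power at 41 per arm is 79.0%. The stated "approximately 80% power is 41 per arm" therefore reproduces for its inputs.

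**2. Reference for the planned test.** After 20% attrition, 50 × 0.80 = 40 per arm are evaluable. Exact two-sided Fisher power for 60% vs 30% at 40 per arm is 72.5%. This, not 80%, is the undiluted comparator at a 60% baseline. The gap between the two comes from the test and the evaluable number, not from dilution.

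**3. Dilution under the section 4 rule.** Arm-level difference = π × (difference in index patients with a treated contact).

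**4. Inputs for π.** The only contact figure contradicts itself: 17/35 = 48.6%, whereas 37% would be 13/35. Both values are carried as q. No distribution of contacts per index patient is given, so k = 1, 2, 3 is assumed, with contacts independent and every colonized contact treated: π = 1 − (1 − q)^k.

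**5. Sensitivity range.** Colonization is halved only where a contact is treated, with the same baseline in both strata. The Arm 1 rate is 0.60 − 0.30π, or 0.80 − 0.40π at the top of section 7's range. Power is exact two-sided Fisher at 40 per arm.

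| k | q | π | Arm 1 (60% base) | Power | Arm 1 (80% base) | Power |
|---|---|---|---|---|---|---|
| 1 | 37% | 0.37 | 48.9% | 13% | 65.2% | 24% |
| 1 | 48.6% | 0.49 | 45.4% | 20% | 60.6% | 39% |
| 2 | 37% | 0.60 | 41.9% | 31% | 55.9% | 56% |
| 2 | 48.6% | 0.74 | 37.9% | 44% | 50.6% | 73% |
| 3 | 37% | 0.75 | 37.5% | 46% | 50.0% | 75% |
| 3 | 48.6% | 0.86 | 34.1% | 58% | 45.4% | 86% |

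**6. Relaxing the equal baseline.** Colonized contacts may re-seed the index patient, so the Arm 2 rate could be higher in patients who have them. Let that rate be a, and let the rate in the others be b. Suppose treating the contacts brings a down to b. Then Arm 1 = b = 0.30 and Arm 2 = πa + (1 − π)·0.30 = 0.60, which gives a = 0.30 + 0.30/π:

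- one contact: 111% (q = 37%, impossible) or 92% (q = 48.6%);
- two contacts: 80% or 71%;
- three contacts: 70% or 65%.

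A 30-point arm-level effect is therefore attainable with two or more contacts.

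**The case against.** The case for the plan has four parts.

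- **The power arithmetic is sound, and 30% is stated as an arm-level rate.** Both are true. A reader might infer that the sample-size formula was misapplied; step 1 shows that it was not. Section 7 also admits that the effect is unknown, and Aim 2 exists to estimate it. What remains is that section 7 does not say the 30% already averages over patients whose contacts go untreated.
- **The section 4 rule may not be the operative one.** The passages in sections 3 and 4 that read as if all members are treated would, if they govern, remove this dilution. That stands. The concern is conditional on the rule, and reconciliation comes first.
- **The carriage input does not describe this population.** It covers sexual partners of 35 subjects whose own MRSA status is not given, from a cohort with 16.8% colonized. Every index patient randomized here is confirmed positive, so contact carriage could be higher. No household rate is given. A reader might infer from the 37% that most of Arm 1 gets the Arm 2 treatment; the documents do not support any particular share.
- **Baseline assumptions drive the numbers.** This also stands. The 80% baseline raises power considerably, and unequal baselines make the planned effect possible with two or more contacts. A reader might infer that 30 points is out of reach in general. That follows only under a halving with equal baselines, where π would have to be 1. The one-contact case stays difficult under step 6, and eligibility permits it, since a single sexual partner suffices.

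**Conclusion.** The concern holds as a gap in the justification, not as an arithmetic error. Section 7 states one power figure for an effect applied to all of Arm 1, makes no allowance for the section 4 no-regimen rule, and gives no usable input for the share affected. Under that rule, and the assumptions of step 5, power runs from 13% to 58% at a 60% baseline and from 24% to 86% at 80%, against 72.5% undiluted at 60% vs 30%. The spread comes from the number of contacts, the carriage rate and the baseline, none of which the documents fix. It would be wrong to quote any one of these values as the trial's real power. This should be fixed, but it does not invalidate the randomized comparison.

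**What to change.** 1. Reconcile the statements in sections 3 and 4 on which contacts are treated. No position is taken here on what the rule should be.
2. Correct 37% against 17/35 in the introductory text, and say whether those 35 subjects were themselves colonized.
3. In section 7, replace the single 80% figure with power for the planned Fisher test over stated ranges of π and of the Arm 2 rate, under the reconciled rule.
4. Keep the comparison of all randomized index patients as primary, and report the observed π with the Aim 2 effect size.
5. Label any comparison restricted to index patients with a colonized contact as secondary and exploratory. Use it only if contacts are screened on the same schedule in both arms, ideally before the allocation envelope is opened. As written, contacts are screened after open-label randomization, with a 14-day window set only for Arm 1, so ascertainment could differ by arm. The subgroup is also small: with one contact, 0.37 × 40 ≈ 15 to 0.486 × 40 ≈ 19 per arm, giving Fisher power of about 23–37% for 60% vs 30%.

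Items 1 to 4 cost wording and a short power table, with no extra patients; the stated power becomes a range, less favourable in most scenarios. Item 5, if wanted, means fixing the timing of Arm 2 contact screening or moving contact screening ahead of allocation.
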